5.1. Research Question

What is the effect of an aerobic physical exercise program on reducing blood pressure, abdominal obesity, altered glucose levels, and increasing HDL in college-level students at the University of Colima?

5.2 Objectives

5.2.1 General Objective

To evaluate the effect of implementing an aerobic physical exercise program on the reduction of blood pressure, abdominal obesity, altered glucose levels, and increasing HDL in college-level students at the University of Colima.

5.2.2. Specific Objectives

1. To establish the prevalence of metabolic disorders (abdominal obesity, triglycerides, HDL, hypertension, and glucose alterations).
2. To determine and compare the post-intervention level of physical activity using the long version of the International Physical Activity Questionnaire (IPAQ).
3. To determine and compare the post-intervention level of cardiorespiratory fitness through the Queen's College Step Test.
4. Compare post-intervention prevalence levels of metabolic disorders (HDL, triglycerides, abdominal fat, hypertension, blood glucose alterations) in higher education students.
5. Determine the level of association between metabolic disorders and cardiorespiratory fitness pre- and post-intervention.

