According to perspectives from Ramos 2020, Lozano 2021, and ENSANUT 2022, nutrition surveys reveal that Mexican higher education students have obesity rates ranging from 48.6% to 72.5%, which is highly detrimental to cardiovascular health, especially when combined with the widespread physical inactivity and sedentary behaviour observed among young individuals (5, 25).

2.3.1. Sedentary lifestyle and physical inactivity as a risk factor in metabolic disorders in higher education students.

The World Health Organization (WHO) and Silveira in 2022 define physical inactivity as failing to engage in 150 minutes of moderate-intensity physical activity or 75 minutes of

vigorous-intensity activity per week. Likewise, they define sedentary behaviour as engaging in activities with a basal energy expenditure equal to or less than 1.5 METs (unit of measurement for metabolic rate or energy consumed while at rest) (annexe 12). Examples of such activities include sitting for long hours at university or home, lying down, looking at a cell phone, or doing desk work (52,57).

According to the PAHO and the National Health and Nutrition Survey (ENSANUT) in 2022, physical inactivity levels in Latin America increased from 33% to 39% (58). In Mexico, there has been a growth from 14% in 2016 to 20.8% in 2018(59). The latest ENSANUT report reveals that 42.6% of adolescents aged 15 to 19 don't accumulate an average of at least 60 minutes per day of moderate or vigorous physical activity (MVPA), 90.8% of them spend >2 hours daily in front of screens, and 48.1% of adolescents aged 14 to 17 do not get the recommended sleep duration for their age (8 to 10 hours per day) (60).

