Arterial Hypertension	Subject's systolic and diastolic blood pressure measured in mercury millimeters (mmHg)	Quantitative Continuous Ratio	It is considered an alteration when: Males > 130/85 mmHg Females > 130/85 mmHg	Sphygmomanometer
Physical Activity Level	Physical Activity performed by the subject 7 days before the survey	Qualitative Ordinal	PA: Low, Medium, High	IPA-Q (International Physical Activity Questionnaire)
Physical Fitness Test: Aerobic	Subject's cardiorespiratory capacity using an	Qualitative Ordinal	Very Poor Poor Average	Quee's College Step Test

Capacity	effort test.		Good Excellent Superior	
----------	--------------	--	-------------------------------	--

Source: self-made based on the reference (11,105).

Table 6. Independent variables

Variable	Operational definition	Nature	Scale	Instrument
Aerobic physical exercise	Individually adapted aerobic physical exercise program meeting the WHO 2021 criteria and the FITT Principles.	Quantitative Continuous Ration	57% - 76%	Prescription

Source: self-made.

Table 7. Intervinient variables

Variable	Operational definition	Nature	Scale	Instrument
Age	Chronological age in years	Quantitative Continuous	18 - 24 years	Survey
Sex	Genetically corresponding sex	Qualitative Dichotomous nominal	Male and Female	Survey

Source: self-made.

8. Location for carrying out the protocol

University of Colima's Sports Center (central campus).

9. Study Procedure

Once the project is approved by the Bioethics Committee from the Faculty of Medicine at the University of Colima (Annex 1) and the Ethics Committee from Colima's Regional Hospital (Annex 2), annexing a no-conflict of interest letter (Annex 3), letters of intent will be prepared and sent to the directors of the faculties within the central campus of the University of Colima (Annex 4). Their purpose is to inform them about the project's generalities, obtain permission to share it with the students and address any questions they may have

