Those who agree will receive an informed consent form (Annex 5) for their respective signatures. They will be informed about the appropriate attire for the study (for women, this includes sports shoes, leggings, and a top or T-shirt, and for men, shorts and a T-shirt), the requirement to fast for a minimum of 8 hours on the data collection day, and the date (Saturdays), time (8:00 am to 12:00 pm) and place (Faculty of Medicine, University of Colima) of the initial tests (these tests will also be considered the baseline for people who are found to have a metabolic alteration).

On assessment day, the project team will execute the following tests: application of the IPA-Q questionnaire (*annexe 6*), abdominal circumference (*annexe 7*), blood pressure (*annexe 8*), blood collection by venipuncture for HDL, triglycerides and glycemia (*annexe 9*), and the Queen's College step test (3 minutes) to determine their cardiorespiratory capacity (*annexe 10*), (after completing all the tests, every participant will receive refreshments and will be asked if they are in good condition to conclude their assessments, if not, they will be monitored until their answer is affirmative).

Once all blood samples are collected, they will be taken to the laboratory at the Faculty of Chemical Sciences, University of Colima, for processing. Simultaneously, data from the other assessments will be synthesized. When the final results from all 5 tests are collected, a sample of 48 subjects will be selected for the protocol, considering the established inclusion criteria (*Table 2*). With this sample, simple randomization will be performed in a new meeting, using sealed envelopes (each containing a letter indicating group assignment that will not be seen by

participants). Participants will draw an envelope and mark it with their names, and they will hand the envelope to the designated person (principal investigator).

At the end of the meeting, the envelopes will be opened by the organizers in the absence of the participants to reveal whether they belong to the (A) control or (B) experimental group. This process ensures single-blind criteria, where participants do not know their group assignment.

[figure not shown]

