After forming the (A) control and (B) experimental groups, they will be divided to provide them instructions for compliance with the exercise program while maintaining single-blind conditions. In the control group (A), the exercise prescription used by Habibzadeh in 2010 will be implemented: which involves walking for 30 minutes at an intensity of 57% to 76% of the maximum heart rate, three times per week (Monday, Wednesday, and Friday) for eight weeks (*annex 11*). They will always be accompanied by a previously trained physical education student (Monitoring the intensity range in which the subjects must be during the session, will be done through the effort perception scale (*Annex 12*), heart rate at 15 seconds multiplied by 4 or the H10 polar monitor) (83). On the other hand, the experimental group (B) will engage in an aerobic exercise program (jogging, aquatic activities, and stationary cycling) lasting 40 to 60 minutes, three times per week (Monday, Wednesday, and Friday) for eight weeks, always under the supervision of the principal investigator. Each participant in the experimental group will receive a structured exercise prescription tailored to their specific condition, considering the established aerobic training ranges (57% to 63% of maximum heart rate) (*annexe 11*). (Monitoring the intensity range in which the subjects must be during the session will be done through the effort perception scale (*Annex 12*), heart rate at 15 seconds multiplied by 4 or the H10 polar monitor).

By the end of the first four weeks, the second round of assessments and samples will be done, taking into consideration: Abdominal circumference (*annexe 7*), blood pressure (*annexe 8*), blood collection by venipuncture for HDL, triglycerides and glycemia (*annexe 9*), and the Queen's College step test will be performed (3 minutes) (*annexe 10*), (after completing all the tests, every participant will receive refreshments and will be asked if they are in good

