condition to conclude their assessments, if not, they will be monitored until their answer is affirmative). Subsequently, after completing sample collection and assessments, the control group (A) will continue with the same dynamics as in the initial weeks. The experimental group (B) will maintain the same exercises (jogging, aquatic activities, and stationary cycling), but their intensity may be adjusted from 64% to 76% of the maximum heart rate if favourable results are obtained from the cardiorespiratory fitness test (*annexe 11*), since this shows the level of evolution of the subject after the initial intervention and thus, the FITT-VP principle in exercise prescription would be fulfilled.

At the end of the last 4 weeks of the aerobic physical exercise program, the same sampling will be concluded; Abdominal circumference (*annexe 7*), arterial pressure (*annexe 8*), blood collection by venipuncture for HDL, triglycerides and glycemia (*annexe 9*), and the Queen's College step test will be performed (3 minutes) (*annexe 10*) (after completing all the tests, every participant will receive refreshments and will be asked if they are in good condition to conclude their assessments, if not, they will be monitored until their answer is affirmative), finishing the proposed intervention protocol.

10. Study flowchart

11. Statistical analysis

The statistical analysis will be conducted using the Statistical Package for the Social Sciences (SPSS) Statistics 26 from Business Machine (IBM). Descriptive statistics will be carried out, including measures of central tendency for the variables of age, sex and IPA-Q. Normality tests will be applied such as Kolmogorov-Smirnov for samples > 50 , and Shapiro-Wilk for samples < 50 . For the levels of triglycerides, glucose, HDL (High-Density Lipoprotein), abdominal circumference, and cardiorespiratory fitness, paired-sample T-tests will be used if the data follow a normal distribution, but if they do not, the Wilcoxon signed-rank test will be employed. To compare the control and experimental groups, independent-sample t-tests will be used if the data is normally distributed, otherwise the Mann-Whitney U test will be used. Likewise, a multivariate analysis will be carried out to relate the influence of physical exercise

on metabolic alterations. A significance level of $p \leq 0.05$ will be considered statistically significant.

12. Ethical considerations

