The purpose of this questionnaire, in its extended version, is to evaluate the level of physical activity and cardiac output of study participants during the last 7 days before completion. This is administered before and after the intervention and is aimed at individuals aged 15 to 69 years (92). Participants will receive a detailed introduction on the purpose of the questionnaire, followed by a step-by-step breakdown of the questionnaire, and will be provided with clarity on how to complete it (minutes or hours). All information will be provided, all questions or concerns of the participants will be answered, and then they will be provided with a designated space with a chair, table, pen, and the corresponding questionnaire to complete it. At all times, participants will have the support of a highly trained professional in the questionnaire, available to resolve any questions that arise during the process.

INTERNATIONAL PHYSICAL ACTIVITY QUESTIONNAIRE (October 2002)

LONG LAST 7 DAYS SELF-ADMINISTERED FORMAT

FOR USE WITH YOUNG AND MIDDLE-AGED ADULTS (15-69 years)

The International Physical Activity Questionnaires (IPAQ) comprises a set of 4 questionnaires. Long (5 activity domains asked independently) and short (4 generic items) versions for use by either telephone or self-administered methods are available. The purpose of the questionnaires is to provide common instruments that can be used to obtain internationally comparable data on health-related physical activity.

Background on IPAQ

The development of an international measure for physical activity commenced in Geneva in 1998 and was followed by extensive reliability and validity testing undertaken across 12 countries (14 sites) during 2000. The final results suggest that these measures have acceptable measurement properties for use in many settings and in different languages, and are suitable for national population-based prevalence studies of participation in physical activity.

Using IPAQ

Use of the IPAQ instruments for monitoring and research purposes is encouraged. It is recommended that no changes be made to the order or wording of the questions as this will affect the psychometric properties of the instruments.

Translation from English and Cultural Adaptation

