***Skip to PART 4: RECREATION,
SPORT AND LEISURE-TIME
PHYSICAL ACTIVITY***

19. How much time did you usually spend on one of those days doing **moderate** physical activities inside your home?

_____ **hours per day**
_____ **minutes per day**

PART 4: RECREATION, SPORT, AND LEISURE-TIME PHYSICAL ACTIVITY

This section is about all the physical activities that you did in the **last 7 days** solely for recreation, sport, exercise or leisure. Please do not include any activities you have already mentioned.

20. Not counting any walking you have already mentioned, during the **last 7 days**, on how many days did you **walk** for at least 10 minutes at a time **in your leisure time**?

_____ **days per week**

No walking in leisure time

Skip to question 22

21. How much time did you usually spend on one of those days **walking** in your leisure time?

_____ **hours per day**
_____ **minutes per day**

22. Think about only those physical activities that you did for at least 10 minutes at a time. During the **last 7 days**, on how many days did you do **vigorous** physical activities like aerobics, running, fast bicycling, or fast swimming **in your leisure time**?

_____ **days per week**

No vigorous activity in leisure time

Skip to question 24

23. How much time did you usually spend on one of those days doing **vigorous** physical activities in your leisure time?

_____ **hours per day**
_____ **minutes per day**

24. Again, think about only those physical activities that you did for at least 10 minutes at a time. During the **last 7 days**, on how many days did you do **moderate** physical activities like bicycling at a regular pace, swimming at a regular pace, and doubles tennis **in your leisure time**?

_____ **days per week**

No moderate activity in leisure time → **Skip to PART 5: TIME SPENT SITTING**

25. How much time did you usually spend on one of those days doing **moderate** physical activities in your leisure time?

_____ **hours per day**
_____ **minutes per day**

PART 5: TIME SPENT SITTING

The last questions are about the time you spend sitting while at work, at home, while doing course work and during leisure time. This may include time spent sitting at a desk, visiting friends, reading or sitting or lying down to watch television. Do not include any time spent sitting in a motor vehicle that you have already told me about.

26. During the **last 7 days**, how much time did you usually spend **sitting** on a **weekday**?

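### Objective 2 needs a post-intervention IPAQ, but the final-visit list in section 9 omits it, and an undated 7-day recall may count the trial's own supervised sessions

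*Combined protocol and SAP*

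**What the plan says.** Objective 2 in section 5.2.2 is "To determine and compare the post-intervention level of physical activity using the long version of the International Physical Activity Questionnaire (IPAQ". Table 5 (section 7) lists physical activity level as a dependent variable, graded low, medium or high, and defines it as "Physical Activity performed by the subject 7 days before the survey".

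The documents give two accounts of when the questionnaire is used:

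- **Annexe 6** says of the IPAQ: "This is administered before and after the intervention".
- **Section 9** lists it at the first assessment. For the last visit it says "At the end of the last 4 weeks of the aerobic physical exercise program, the same sampling will be concluded" and then names abdominal circumference, blood pressure, blood sampling and the step test. The IPAQ is not among them.

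Part 4 of the questionnaire asks about activity in the last 7 days done "solely for recreation, sport, exercise or leisure". Nothing in the annexe tells participants or scorers to leave out trial sessions. Section 11 mentions the IPAQ by name only among the variables to be described.

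**The concern.** There are two linked problems.

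The first is practical. Section 9 is the operating schedule. A team that follows its final list would finish the trial without the measurement that objective 2 requires, and recall of that particular week cannot be recovered later.

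The second is interpretive. At baseline nobody has been assigned any exercise. If the IPAQ is completed soon after the last session, the recall week contains the exercise the trial itself supplied. Attendance at assigned sessions could then be reported as though students had become more active. If the arms are assigned different weekly minutes, part of any between-arm difference would come from the same source.

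**Working it through.** The plan gives no figure of its own for the IPAQ; its sample size is built on triglycerides and does not bear on this point. The check is a comparison of the visit lists and a count of supervised minutes.

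**Step 1. Visit lists.**

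| Source | IPAQ at baseline | IPAQ after the programme |
|---|---|---|
| Objective 2 | not stated | required |
| Annexe 6 | yes | yes |
| Section 9 | yes | not listed |

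Objective 2 and Annexe 6 agree with each other. Section 9 does not agree with them.

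**Step 2. Supervised minutes per week.** Minutes = sessions per week × minutes per session, with three sessions a week (Monday, Wednesday, Friday).

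| Source | Control | Experimental | Experimental minus control |
|---|---|---|---|
| Section 9 | 3 × 30 = 90 | 3 × 40 = 120 to 3 × 60 = 180 | 120 − 90 = 30 to 180 − 90 = 90 |
| Annexe 11, Tables 11 and 12 | 3 × 60 = 180 | 3 × 60 = 180 | 180 − 180 = 0 |
| Baseline | 0 | 0 | 0 |

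With full attendance and a window that covers the whole final week, the pre-post change therefore contains 90 to 180 minutes a week of assigned exercise, depending on arm and on which section is followed.

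**Step 3. How much falls in the recall window.** This depends on the completion date, which is not given. Take the last session as a Friday and count the seven days before the day of completion:

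- Completed 1 to 3 days later: all three sessions are in the window.
- 4 to 5 days later: two sessions.
- 6 to 7 days later: one session.
- 8 or more days later: none.

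Section 9 puts the initial tests on Saturdays. If the final tests are also on a Saturday, the day after the last session (an assumption; the protocol says this only of the initial tests), all three sessions count and the minutes in step 2 apply in full.

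**The case against.** The strongest reply is that a post-intervention IPAQ is clearly planned. Annexe 6 says so, and section 9 points to that annexe when it introduces the questionnaire. The flowchart in section 10 and the test distribution in Annexe 15 are not readable in the text available for this review and may show it. This stands: a reader might infer from section 9 that objective 2 will have no data, and the documents do not support that. They support an inconsistency that puts collection at risk.

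A reader might also count the mid-programme visit as a gap. It is not one, because objective 2 asks only for a post-intervention level.

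It is also tempting to say that the sessions alone lift every adherent experimental participant over the protocol's inactivity limit, defined in section 2.3.1 as "failing to engage in 150 minutes of moderate-intensity physical activity". The documents do not bear this out. At section 9's lower duration, 3 × 40 = 120 minutes. Table 4 accepts 19 of 24 sessions, so an adherent participant may miss one in the final week: 2 × 60 = 120. That limit is also background material rather than the trial's IPAQ grading, and nothing in the documents shows that the sessions would move anyone between low, medium and high.

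Finally, the IPAQ also covers work, transport and housework, and total activity is a legitimate reading of objective 2. This stands too: the score would be partly, not wholly, the assigned programme, and replacing the total by a net score would be a preference. What the reply does not remove is the missing item in section 9, the missing date, and the absence of any rule on supervised sessions.

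**Conclusion.** The point holds in a limited form. Without condition, section 9's final-visit list conflicts with objective 2 and Annexe 6.

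The recall problem is conditional on the IPAQ being completed before a full 7-day recall period has passed since the last session. With all three final-week sessions attended and inside the window, the answers include 90 minutes (control) and 120 to 180 minutes (experimental) by section 9, or 180 minutes in both arms by Annexe 11, against 0 at baseline. A pre-post rise would partly reflect those sessions under either set of durations. A between-arm artefact of 30 to 90 minutes a week arises only under section 9's durations and is nil under Annexe 11's.

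These figures assume that participants report the sessions and that final-week durations are as written. The note under Table 12 allows volume to be adjusted after the first four weeks. This is a secondary objective, so the matter should be corrected but does not threaten the main comparison.

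**What to change.** - Add the IPAQ to the end-of-programme list in section 9.
- State its date relative to the last supervised session.
- Record attended minutes for each session. The protocol sets an attendance threshold and monitors intensity but does not say that minutes are logged.
- Leave the questionnaire wording unchanged, and report the result twice: in total, and excluding supervised sessions. Do not interpret a rise in the total as a change in habitual activity.
- Reconcile the session durations in section 9 and Annexe 11, since the size of any between-arm artefact depends on them.

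The cost is one questionnaire at an existing visit, a minutes log, and a second scoring. The weakness is that the net score relies on participants having reported the sessions: subtracting logged minutes that were never reported would understate activity and could give negative values. That is a reason to show both results rather than the net score alone.
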